### **Secondary analyses.**

In the context of the test of the model in Figure 4, we will conduct secondary analyses to test whether there are effects of methylation on network connectivity and of inflammation on BOLD activation. We will also conduct exploratory analyses to determine whether the treatments are differentially effective by gender, age, or race/ethnicity, and we will explore interactions between mechanisms with appropriate Type I error correction. Finally, we will examine the relationship of early changes in drinking behavior (within the first 2 weeks) and neural adaptations in the analysis plan and how the degree of mindfulness uptake relates to neural and clinical outcomes.

### **Project Timeline.**

The proposed timetable for all data collection, analysis, and manuscript preparation is five years. Because the protocol is similar to clinical protocols we have used in previous studies and because we have existing experienced staff, we will only need 3 months to refine and implement the protocols. Thus, data collection will begin in earnest in April 2016. Consistent with previous trials, we expect to enroll about 6 patients per month during the first year and about 4 per month thereafter. Thus, we expect to enroll 50 patients during each of the first 4 years and 26 patients in the last year, for a total of 226 patients. The remainder of year 5 will involve data analysis and manuscript preparation.

---

## **V. FUNDING**

This study is funded by a grant from NIAAA.

## **VI. ABOUT THE SUBJECTS**

---

Participants for the proposed research are 226 individuals with an alcohol use disorder who will be recruited from the greater Denver/Boulder metropolitan area in the state of Colorado using the exclusionary criteria described below.

### **Criteria for inclusion in the study are:**

1. Must be between the ages of *21 and 60* and provide informed consent;
2. Have a primary DSM-V diagnosis of alcohol use disorder;
3. Must be within 10 days of last drink;
4. Must have been drinking heavily (criteria dependent upon individual's age, gender, and BMI) for a consistent period of time;
5. Must have a breath alcohol level of 0 at screening (to sign consent form);
6. Not currently taking any medications for the treatment of psychiatric disorders, including substance use disorders, mood disorders, and psychosis;
7. Female subjects must not be pregnant, as indicated by a pregnancy test which will be administered at baseline (tests will be re-administered at the 32 week session prior to the MR scan);
8. Must not be positive for sedatives, opiates, cocaine, or amphetamine on drug screen at baseline;
9. Must not meet criteria for psychotic disorder, bipolar disorder, or a major depressive episode;
10. Must not have a Beck Depression Inventory (BDI) score of more than 28 (29-63 indicates severe depression);
11. Must not rate 2 or higher on BDI question 9 (assessment of suicidality);
12. Must have a Clinical Institute Withdrawal Assessment (CIWA) score less than 8 (indicating no need for medical detox). If CIWA is greater than 8, patient will be referred to detox and only accepted into study after detox is successfully completed.
13. Must have expressed a desire during their initial screen to reduce the number of drinks they regularly consume

## **VI. VULNERABLE POPULATIONS**

---

This study does not include any vulnerable populations.

## **VII. RECRUITMENT METHODS**

---

Advertisements in mass media outlets (e.g., newspaper, radio); through social media (e.g., Facebook); using online recruitment tools (e.g., ResearchMatch); via flyers given to local mental health providers, who offer limited or no substance use treatment (e.g., referrals for alternative treatment options [when alcohol is the primary presenting concern] or as an adjunct alcohol treatment [when the provider is addressing other mental health issues]); and direct mailings targeting the greater Front Range metropolitan area, which includes Boulder County, Denver, and suburbs of Denver, will be the primary sources of participants. Additionally, participants will be able to fill out an online screening showing their interest that will be directly advertised via a link to Redcap

on the mailings sent out. The online screening will be administered through Redcap and is password protected. Only the research team knows the password to this Redcap screening. This recruitment strategy is based on the successful recruitment in our previous trials. All of these advertisements will describe the opportunity to earn a maximum of \$340 by participating in a study exploring mindfulness and biological mechanisms related to alcohol use. Men and women of all ethnic backgrounds will be recruited into the study. We expect that the proposed study will reflect the ethnic diversity of the greater Denver metropolitan area, such that approximately 25-35% of the final sample will represent Latino and non-Caucasian individuals. We will recruit 226 individuals. Our previous experience with clinical trials (e.g., Littlewood et al., 2014), as well as the experience of our research team members ([name], [name], [name]) with this specific intervention supports the feasibility of recruiting approximately 50 patients per year (see [name] et al., 2014)

During the phone or online interview, participants will be screened for the inclusion criteria outlined above. Before asking any eligibility questions, the interviewer will obtain verbal consent from the potential participant. For the online interview, participants will be marking their electronic written consent to participate in the screening at the beginning of the survey. The potential participant will also be informed that some of the questions asked will concern their use of substances including alcohol, cannabis and illegal drugs. They will be told that they do not have to answer any question that makes them feel uncomfortable; however, not answering some or all of the questions on the phone or on the online screening, may result in their being ineligible to participate in the study. In accordance with the IRB's guidelines for pre-screening potential participants () only first names or initials will be collected to identify the potential participant during this phone screen (pre-screen). In regards to the online phone screen, the potential participant will be contacted on the phone after they complete the screen in order to receive an explanation about the study and to schedule them for their first appointment. For participants that do not meet criteria, they will be sent an email stating their ineligibility and will receive resources for alcohol and mindfulness therapies in their area. In order to protect participant confidentiality, the first eight pages of the phone screen form will be shredded immediately after the phone screen (pre-screen) is complete. Only the information relevant to contacting the participant on the phone screen will remain. This contact information will be important for us to retain so that we can reach participants concerning their appointments. Participant contact information will be stored in a separate research folder, apart from all other study documents. This folder will be stored in a locked filing cabinet CU CHANGE research lab at the Center for Innovation and Creativity (CINC). Each contact information sheet will be destroyed at the end of the study, which will minimize any risk of loss of confidentiality. For the online phone screen, the participant information will be kept on a password protected Excel document on a computer in [name] laboratory which will be destroyed at the end of the study.

Due to the COVID-19 situation we are collecting remote data only and will return to our original protocol when it is safe to do so. The remote RECRUITMENT METHODS will be as follows:

Participants will be recruited using social media advertising and will go through a phone screen with a research assistant to confirm their eligibility and answer any questions they may have. If the participant is eligible, they will be scheduled for their next Zoom appointment.

## **VIII. COMPENSATION**

---

We estimate that the completion of assessments and procedures across the duration of the trial, including therapy sessions, will total approximately 16 hours of time (an additional 2 hours for MRI). To compensate subjects for their time and travel costs, subjects who will not be scanning will be paid a maximum of \$280 if they complete all therapy sessions and appointments and those subjects who will be scanned will be paid a maximum of \$340. As a breakdown for compensation participants will be given:

- \$30 for completing the Baseline Session (an additional \$30 will be given to participants who undergo the first MRI scan)
- \$30 at the Intermediate Session (week 4)
- \$30 for completing the End of Treatment Session (week 8)
- \$15 for each therapy session they attended (week 1-3 and 5-7) (\$90 total; will be given in total to participants at week 8)
- \$50 for completing the full week 20 follow-up (\$30 will be given for completing surveys, whether completed in our laboratory or remotely; \$20 will be given for blood sample collection, which can only occur in our laboratory)
- \$50 for completing self-report measures for the week 32 follow-up (\$30 will be given for completing surveys, whether completed in our laboratory or remotely; \$20 will be given for blood sample collection, which can only occur in our laboratory; an additional \$30 will be given to participants who undergo the second MRI scan)

Due to the COVID-19 situation we are collecting remote data only and will return to our original protocol when it is safe to do so, the remote COMPENSATION will be as follows:

Compensation (via Amazon gift cards) for each study appointment goes as follows:

- Baseline session: \$30
- Therapy sessions (weeks 1-3, 5-7): \$15 per session (\$90 total given at week 8)
- Intermediate session (week 4): \$30
- End of treatment session (week 8): \$30
- Follow-up session I (week 20): \$50 for surveys
- Follow-up session II (week 32): \$50 for surveys

## **IX. CONSENT PROCESS**

---

Given that the phone screen portion of the study presents no more than minimal risk of harm to subjects and involves no procedures for which written consent is normally required outside of the research study, the study team is requesting a waiver of written consent for the phone screen portion of the study. The member of the research team who is conducting the phone screen will say the following prior to asking any screening questions, in order to obtain verbal consent to conduct the screen: "Thank you for your interest in our research study investigating alcohol and mindfulness. Do I have your verbal consent for me to ask you a few questions to verify that you are qualified and tell you about the requirements before you come to the lab? It will take about 10-15 minutes of your time. If you have any questions you can contact [name] at [contact] or the Institutional Review Board at [contact]. Your participation in this pre-screening is voluntary." The member of the study team will be available to answer any questions regarding the phone screen process, and the phone screen

will be immediately discontinued if the potential participant does not give verbal consent to answer the eligibility questions. For the online screening, the participant has the choice to exit out of the screening at any point without completing it. The study team will track individuals who give verbal consent to the phone screen in a non-identifiable manner (i.e., subjects who consent to be phone screened will be referred to as Subject-01, Subject-02, etc. on the tracking log). This tracking log will be stored in a password-protected file on a computer in [name] laboratory.

When a participant arrives for his/her first session at the Center for Innovation and Creativity (CINC), a member of the research team (i.e., a trained research assistant or graduate student) will greet him/her in the first-floor lobby. The research assistant will take the participant to a private room and provide the participant with a copy of the informed consent document. A description of the MRI procedures is included in the consent form, and all participants will be given a verbal description of the MRI screening process and potential risks of MRI studies. Prior to asking the participant to sign the consent form, the trained research assistant and the participant will have a discussion regarding the research study. Additionally, the research assistant or graduate student will be available to answer any questions he or she may have about the study. Participation will be clearly stated as voluntary, with the option to withdraw at any time. There will be no deception involved with this study. After discussing the study and going over the consent form with the researcher, the participant will initial and sign the informed consent document.

Separate signatures will be obtained for participation in the study and broadly sharing gut metagenomic and phenotypic data. Individuals who opt not to have their gut metagenomic and phenotypic data broadly shared will still be allowed to proceed with participation in the study.

Due to the COVID-19 situation we are collecting remote data only and will return to our original protocol when it is safe to do so. The remote CONSENT PROCESS will be as follows:

When a participant arrives via Zoom for his/her first remote Baseline & consent session a member of the research team (i.e., a trained research assistant or graduate student) will greet him/her and welcome them to the study. The research assistant will provide the participant with a copy of the informed consent form via a link to the DocuSign document. Prior to asking the participant to sign the consent form, the trained research assistant and the participant will have a discussion regarding the research study. Additionally, the research assistant or graduate student will take the participant through the informed consent document, step by step, and give them an opportunity to ask any questions about their participation in the study. Participation will be clearly stated as voluntary, with the option to withdraw at any time. There will be no deception involved with this study. After discussing the study and going over the consent form with the researcher, and after all questions have been resolved, the participant will then show their ID to the researcher, over Zoom, to confirm they are between 21-60 years old. Then the research assistant will use DocuSign to electronically sign the consent form and send it to the participant to sign. The participant will then send the signed DocuSign informed consent form back to the researcher. Signed consent forms will be stored securely on our server in a password protected folder.

## **X. PROCESS TO DOCUMENT CONSENT IN WRITING**

---

In accordance with 45 CFR 46.117, an unsigned copy of the form used to document consent will also be given to the study participant.

## **XI. PROCEDURES**

---

### **Screening for Eligibility/Scheduling**

Participants will contact the researchers with their interest by phone, e-mail or by filling out the online screening. The researcher will respond with an overview of the study and answer any questions the potential participant has before screening the caller for preliminary eligibility. In the case that a potential participant requests more information via e-mail, the research assistant responding to the e-mail will ask the participant to call the lab phone number (same phone number provided on all study advertisements) for more information, or e-mail the study team a phone number at which the potential participant could be reached at and a desirable time for the research staff to call. Prior to being asked the phone screen questions, potential participants will be required to give their verbal consent, or in the case of the electronic online screening, written consent. They will be asked to state that they are willing to answer questions over the phone or through the online survey which will help researchers to determine their eligibility to take part in the study. The phone screening process will help to ensure participants have ample opportunity to be informed of the main study components, ask questions, and decide if they are willing to participate before they sign up for the study. For participants that complete the online screening, a research assistant will follow up with the participant on the phone to answer any questions and ask if the participant is willing to take part in the study. If the participants meet the study criteria during the initial phone interview or online screening, they will be invited to come to the CINC for the initial consenting session. They will be given the option of combining this session with the experimental baseline session. If participants choose to do a separate session for consenting, they will schedule their experimental baseline session upon completion of the consent/orientation session. Upon scheduling their first appointment, participants will be provided, via an e-mail attachment (see pre-appointment e-mail template), a letter that will include the time and date of the appointment. If participants are electing to combine both appointments, they will be instructed ahead of time not to drink alcohol within 48 hours, smoke marijuana within 48 hours, or consume caffeine or smoke cigarettes within 3 hours of the session. They will receive an email containing this information upon scheduling the session (see "Instructions for Appointment" document). If participants are doing the consent/orientation and study appointments on two separate visits, they will be given these instructions during the consent/orientation session.

**COVID-19:** Before interacting with research assistants, eligible participants will be asked additional questions related to COVID-19. These questions will be administered prior to any in-person appointment and by a research assistant over the phone (or at a distance of at least 6-feet if the participant is unable to complete the questions over the phone). These questions will be administered to protect staff and participants from the spread of COVID-19. The questions are a precaution based on current university and Centers for Disease Control and Prevention guidelines and may need to be updated as the understanding of COVID-19 evolves. These procedural questions are temporary in nature and will be lifted once university guidelines deem it unnecessary.

### **Informed Consent Appointment**

Upon arrival for the informed consent appointment, participants will be met by a research assistant or graduate student who will escort them to a private consultation room where participants will be asked to complete and sign the informed consent form. If the participant is doing the consent and experimental baseline session in two separate visits, he or she will be informed at the consent session to refrain from drinking alcohol within 48 hours, smoking marijuana within 48 hours, or consuming caffeine or smoking cigarettes within 3 hours of the experimental baseline session, and the baseline session will be scheduled at the end of the consent appointment. The participant will also be given a copy of the Instructions for Appointment Document at the end of the consent visit. If the participant is doing the consent session and experimental session in the same visit, he or she will proceed with the study procedures after completing the informed consent process with the trained research assistant or graduate student.

### **Baseline Session**

After arriving at the lab, qualified participants will (1) complete an informed consent form, and then (at either the same session or a separate session), participants will (2) complete a breath alcohol test, (3) complete a urine toxicology screen, (4) provide a blood sample for assays of peripheral inflammatory markers and DNA methylation, (5) fill out the baseline questionnaires, (6) and take several neurocognitive tasks. Participants will also be given a gut microbiome sample collection kit at the end of the session and will return it to their first scheduled session (7).

Subjects will be breathalyzed before every session starts, including all therapy sessions. Any subject that has a positive BAL or who reports drinking will be rescheduled for that appointment. A participant who blows a BAC over 0.00 will be given one chance to reschedule his/her appointment for the next day. If s/he comes in the next day with a breath alcohol greater than 0.00 then this session will be counted as “missed.” If a subject accumulates more than one “missed” session, they will be automatically dropped from the study on the grounds that they failed to follow explicit study directions properly. Participants will not receive compensation if a session is terminated due to failure to follow the abstinence instructions. They will be informed of this contingency during the phone screen, consent visit and is stated the consent form.

A urine toxicology screen will be administered to insure that subjects have not recently used illicit drugs including, sedatives, opiates, cocaine, or amphetamines.

A member of our research team who has completed a certified training in phlebotomy will collect the blood sample. The blood draw procedures will involve collecting venous blood (40 ml) venipuncture of a peripheral arm vein using standard, sterile phlebotomy techniques. The samples will be tested for cytokine levels and epigenetics using equipment at the CINC.

Subjects will then complete baseline questionnaires related to their demographics, history of drinking, smoking and drug use, and alcohol craving (measures listed below). Also, subjects will take six neurocognitive tests using the NIH toolbox application, which will assess their cognitive function in terms of memory and attention. If not eligible for the MRI, subjects will be randomly assigned to receive MBRP or RP for the next 8 weeks at the end of their baseline session and will also be given their microbiome sample collection kits at the end of the session. They will return the sample kits at their next scheduled session. Subjects will be compensated \$30 for completion of the baseline appointment.

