#### **Specific Aim 1 - Detecting Treatment Effects on Drinking Outcomes.**

The effect of the treatment on alcohol use outcomes (HYPOTHESIS 1) will be analyzed with a 2 (**Treatment:** 8 weeks of MBRP vs. 8 weeks of RP) x 5 (**Time:** Baseline, 4, 8, 20, 32 weeks) mixed general linear model with Heavy Drinking Days (HDD) as the primary outcome variable. We will also examine drinks per drinking day, ICS score, and liver function tests as dependent measures in each of 2 additional models, respectively. In the main analysis with HDD, a significant overall test of the treatment X time interaction will be followed by planned contrasts within the mixed model that allow us to test the superiority of MBRP over RP at the 8, 20, and 32 week follow-up points specifically. The FIML estimation procedure implemented in these analyses will allow us to utilize an “intent to treat” approach such that all subjects who are randomized will be included in the analyses (Schafer & Graham, 2002). It may be that the treatments are equally effective on drinking outcomes, and thus we will not see a direct effect of treatment on outcomes. Even in this case, it is possible that the mechanisms through which the treatments had their impact may differ. Thus, tests of Specific Aims 2 and 3 are still important and warranted.

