### **Follow-up Assessment I (20 weeks)**

At this follow-up session, all subjects will take a BAC test, complete a set of self-report outcome measures and provide a blood sample. Subjects will be compensated \$50 for completing this assessment (\$30 for completing self-report measures and \$20 for providing blood samples). For subjects who are unable to come into the laboratory, the option of completing self-report measures online (via Qualtrics) will be provided for a \$30 compensation.

Participants who are unable to come into the laboratory will be sent an email, with an anonymous link to the same Qualtrics survey that would be administered at the follow-up assessments. All surveys are administered via Qualtrics and, thus, participants will already be familiar with navigating this online survey. The email will include the following instructions:

As our study staff noted, your progress since finishing treatment is extremely important for us to understand how alcohol treatments work, and why they may work better for some individuals than others. Therefore, regardless of whether you feel you have improved, declined, or had no changes since completing treatment, your responses are equally valuable. To reimburse you for your time, we will provide a \$30 gift card.

If you choose to proceed, here is the link to your survey: [INSERT LINK]

After clicking the link, please enter your study ID and treatment condition (see below). Please fill out this survey alone to ensure focus and anonymity. In addition, you may discontinue participation or refuse to answer any questions without penalty. Once you have completed the survey, study staff will be notified and you will receive your compensation within one week.

Your study ID is: [INSERT ID]

Your treatment condition is: [INSERT MBRP or RP]

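### The breath-test rule can leave the primary outcome uncollected because of current drinking at in-person outcome visits; the loss looks small among participants who stay in the study

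*Combined protocol and SAP*

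**What the plan says.** The rule is in the protocol's Procedures, under Baseline Session, but it is not limited to baseline: "Subjects will be breathalyzed before every session starts, including all therapy sessions". Its steps are:

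- **Trigger.** "Any subject that has a positive BAL or who reports drinking will be rescheduled for that appointment". No time window is given for self-reported drinking.
- **Retry.** "A participant who blows a BAC over 0.00 will be given one chance to reschedule his/her appointment for the next day".
- **Missed session.** "If s/he comes in the next day with a breath alcohol greater than 0.00 then this session will be counted as" missed.
- **Removal.** With more than one missed session, "they will be automatically dropped from the study on the grounds that they failed to follow explicit study directions properly".

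The Intermediate Session (4 weeks) and End of Treatment (8 weeks) sections include a BAC test. Follow-up Assessment I (20 weeks) says "At this follow-up session, all subjects will take a BAC test, complete a set of self-report outcome measures and provide a blood sample", and Follow-up Assessment II (32 weeks) follows the same pattern. The instrument table schedules the TLFB, with 30-day recall, at baseline and at these four visits. HDD, the primary outcome, is taken from it. The Specific Aim 1 analysis uses a mixed model with FIML on all randomized subjects, with planned contrasts to "test the superiority of MBRP over RP at the 8, 20, and 32 week follow-up points specifically".

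Online self-report is offered at weeks 20 and 32 to people who cannot attend the laboratory. No such route is stated for in-person weeks 4 and 8. The temporary remote (COVID-19) procedures list no breath test.

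**The concern.** Under the rule, whether HDD is recorded at a visit can depend on drinking around that same visit. FIML gives valid estimates when missingness is explained by observed data. Here the cause is the unobserved current value, so earlier visits explain it only in part. The checks under The impact of attrition and Differential attrition analyses compare baseline measures, so they would not reveal it, and no sensitivity analysis for data missing not at random is planned. If one arm drinks more, it loses more high values, and a true difference is understated. The rule also fits poorly with a treatment model that does not require abstinence (MBRP and RP Implementation) and with the stated intention to analyse everyone randomized.

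**Working it through.** **The plan's own figure.** Power for Specific Aim 1 uses f = .10, 5 time points, correlation .50 and N = 180. The noncentrality is 180 × 5 × 0.10² / (1 − 0.50) = 18, with 4 and 712 degrees of freedom, which gives power .942. This agrees with the stated power of well over .90. If 5, 10 or 20 percentage points of 226 were lost beyond the planned 20%, power would be .926, .906 or .851. The issue is therefore bias, not power.

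**From positive test to lost value.** A first positive test moves the visit by one day. With 30-day recall, HDD is then almost unchanged. Loss requires a second positive test, and it occurs because no text preserves the TLFB at a missed session.

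**Size among participants never removed.** The documents give no positive-test rate, so these inputs are assumptions:

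- HDD out of 30 is beta-binomial (a + b = 1.3), with mean 9.0 for RP and 6.6 for MBRP, a true difference of 2.40. The SDs are about 9.3 and 8.4.
- The chance that a session is missed is m = q × HDD/30, with q = .2, .4 or .6.
- There are 11 sessions after baseline: goal-setting (1), weeks 1 to 8 (8), and weeks 20 and 32 (2).
- HDD is stable across sessions, and misses are independent given HDD.

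A participant is never removed if at most one session is missed: S = (1 − m)¹¹ + 11m(1 − m)¹⁰. The chance of staying in and missing one given visit is L = m(1 − m)¹⁰. With E the average over the HDD distribution in an arm, the share of HDD values missing at a visit is E[L]/E[S]. The true mean in this group is E[HDD × S]/E[S], and the observed mean is E[HDD × (S − L)]/E[S − L].

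| q | Removed, RP / MBRP | HDD missing per visit among never removed, RP / MBRP | Arm difference in that group, true → observed | Shrinkage |
|---|---|---|---|---|
| .2 | 18% / 12% | 2.3% / 1.8% | 1.79 → 1.76 | 1.6% |
| .4 | 35% / 25% | 2.4% / 1.9% | 1.05 → 1.03 | 2.1% |
| .6 | 44% / 33% | 2.4% / 1.8% | 0.66 → 0.65 | 2.2% |

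The per-visit loss hardly changes with q. A higher rate of positive tests mostly moves people from one missed session to removal, and the group that stays drinks less.

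**Does conditioning on earlier data remove the bias?** In a separate simulation, the true standardized difference was .23, the baseline correlation .50, and 10% of values were lost. The baseline-adjusted estimate was .232 when loss was unrelated to drinking. It was .217 and .202 when the log-odds of loss rose by 1 or 2 per SD of current drinking. Adjustment leaves bias in the same direction. The 10% is illustrative, not an expected rate.

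**The case against.** The strongest reply is that the rule reschedules and does not discard, and that much of the apparent harm comes from over-reading it. Several stronger readings are tempting:

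- **Any positive test loses HDD.** The text does not say this. One next-day retry is allowed, and a one-day shift barely matters to a 30-day recall.
- **Any past drinking blocks an outcome visit.** The self-report trigger has no window, but it stands beside a positive breath test, and the only stated abstinence period before a session is 48 hours before baseline. Only a positive retest makes a session missed. The missing window is a wording gap to close, not an established route of loss.
- **The heaviest drinkers are the ones lost.** The rule selects on alcohol near the visit, which is related to HDD over 30 days but is not the same.
- **Losses of 6% to 18% in RP and 4% to 13% in MBRP, with 5% to 20% attenuation.** The same model gives these if every visit is lost independently with probability m and nobody is removed. That contradicts the protocol: anyone who stays in can have at most one missed session. It also compares raw means, whereas the planned mixed model uses the other visits.

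All four replies stand. Two further mitigations stand in part. The online route at weeks 20 and 32 could serve, but its wording does not cover someone who attended and tested positive. The remote procedures avoid the problem, but the protocol intends to return to in-person visits. Week 4 enters the model but is not a superiority contrast. None of this supplies the missing statement that self-report is still collected at a missed session.

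**Conclusion.** The concern holds as a gap in outcome collection. The rule reaches the in-person outcome visits, a second positive test makes the session missed, and no text preserves the TLFB. HDD can then be missing because of current drinking, including at the week 8, 20 and 32 contrasts, and the planned analysis does not correct for it. Among participants who remain in the study, the likely size is small: about 2% of HDD values per visit and about 2% shrinkage of the arm difference. This rests on the assumed HDD distribution, stable drinking, independent misses and q from .2 to .6. The removal percentages in the table depend strongly on q and are not forecasts. They show only that substantial loss under this rule would come mainly from removal after more than one missed session, which is a separate matter.

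**What to change.** In Baseline Session, and in the sections for weeks 4, 8, 20 and 32, state that the TLFB and the other self-report outcomes are obtained whatever the breath-test result. Collect them at the rescheduled contact or by the existing Qualtrics link, with the 30-day window anchored to the scheduled visit date. Extend the wording of the online option to cover this case, and to cover in-person weeks 4 and 8.

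Reconcile the self-report trigger with the purpose of the outcome visits and with the statement that abstinence is not required, so that reported past drinking does not block outcome collection. How therapy, blood draw, neurocognitive tests and MRI are handled after a positive test is for the sponsor to settle.

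The cost is protocol wording. Some TLFBs will be slightly late and without same-day blood. The online survey already exists.
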